6.1.5. Medical/Surgical Procedures

The frequency and percentage for each EGPA therapy (i.e., plasma exchange therapy, operation therapy and other therapies) will be summarized by the retrospective period, the observation period and the follow-up period. This will be based on the ASE.

6.1.6. Pregnancy

All pregnancy of participants and their partners during the study will be listed, based on the TP.

6.1.7. Additional Analyses Due to the COVID-19 Pandemic

A participant is defined as having a suspected, probable or confirmed COVID-19 infection during the study if the answer is "Confirmed", "Probable" or "Suspected" to the case diagnosis question from the COVID-19 coronavirus infection assessment eCRF. The number and percentage of participants with a suspected, probable or confirmed COVID-19 infection, and of COVID-19 test results will be summarized for the TP.

6.2. Appendix 2 Data Derivations Rule

6.2.1. Criteria for Potential Clinical Importance

Not Applicable

6.2.2. Study Period

Assessments and events will be classified according to the time of occurrence relative to the study period.

Screening period is defined as 0-4 weeks before the date of dose of Nucala at Week 0.

Observation period is defined as time from the date of dose of Nucala at Week 0 to the stop date of Nucala +28 days for the participants who did not withdraw from study, or the first treatment discontinuation date +28 days for the participants who withdraw from study. If the date of dose of Nucala at Week 0 is missing, the latest available date between the screening visit date and the Week 0 visit date will be used for the start date of the observation period. When the last Nucala stop date is missing, the last Nucala start date will be imputed.

Follow-up period is defined as time from the first treatment discontinuation date +29 days to 96 weeks within the observation period at maximum. The follow-up period is only applicable for the participants who discontinued the treatment.

Retrospective period is defined as time (within 12 weeks) before the first dose of Nucala. For data of hospitalization for EGPA-related events and ER/Unscheduled visit for EGPA-related events the period is defined as time (within 48 weeks) before the first dose of Nucala.

The study periods to use for summaries on each endpoint are as below.

A:	PMS period	B: Observation period
Retrospective		
period		

Participants who completed the study

Participants who discontinued and moved to the follow-up period

C:	PMS period	D: Observation	E: Follow-up
Retrospective		period	period
period			

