#### Follow-up period

The follow-up period is only applicable to participants who have discontinued the treatment of Nucala due to any reason. The assessments in the routine clinical practice during the follow-up period are shown in Section 9.1 (Appendix 1).

In case EGPA symptoms are deteriorated in a participant who previously discontinued the treatment of Nucala due to improvement of EGPA symptoms, the participant can receive the re-treatment of Nucala during the follow-up period. The participant who received the re-treatment of Nucala continues the assessments in the follow-up period.

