6.2.3. Study Day and Nucala Stop Date

The study day will be calculated relative to visit date of Week 0 and as the number of days from Week 0:

- Ref Date = Missing then Study Day = Missing
- Ref Date < Week 0 then Study Day = Ref Date Week 0
- Ref Date \geq Week 0 then Study Day = Ref Date (Week 0) + 1

The duration of exposure to Nucala is calculated as (Nucala stop date – Nucala start date + 29). If overall Nucala stop date is missing, the last Nucala start date will be imputed.

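### For participants who stop and later restart Nucala, the SAP's observation and follow-up periods overlap on the natural reading, and time off drug counts as exposure

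*SAP*

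**What the plan says.** SAP 6.2.2 has two rules for the end of the observation period. It runs "to the stop date of Nucala +28 days for the participants who did not withdraw from study", or to "the first treatment discontinuation date +28 days for the participants who withdraw from study". The same paragraph adds: "When the last Nucala stop date is missing, the last Nucala start date will be imputed". On follow-up it says: "Follow-up period is defined as time from the first treatment discontinuation date +29 days to 96 weeks within the observation period at maximum".

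Restarting is foreseen. Under the follow-up period in Protocol 3.1, after a stop for improvement followed by deterioration, "the participant can receive the re-treatment of Nucala during the follow-up period", and: "The participant who received the re-treatment of Nucala continues the assessments in the follow-up period". SAP 1.2 repeats this. SAP 6.1.1 counts someone who stops Nucala but remains in the study as a study completer, so the withdrawal rule does not apply to a restarter who stays.

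SAP 6.2.3 defines exposure as stop date minus start date plus 29 and says: "If overall Nucala stop date is missing, the last Nucala start date will be imputed". The offsets in SAP 4.3.1.2.3 and 4.3.1.2.4, for participants who enter follow-up, run from the start of Nucala to its end plus 28 days. Neither formula removes a treatment gap.

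**The concern.** For someone who stops once, the rules fit together: observation ends at stop + 28 days and follow-up starts the next day. For a restarter they use different anchors, the last stop for one period and the first stop for the other. No rule assigns a day or an event to a single period when both apply.

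Three sets of results are exposed.

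- **Summaries given for both periods.** Relapse (SAP 4.3.1.2.2), clinical symptoms (4.3.1.2.1), concomitant medications (6.1.4) and procedures (6.1.5) are presented for observation and for follow-up. One restarter's record can appear in both.
- **Observation-period and on-treatment results.** Adverse events, hospitalizations and emergency or unscheduled visits after the first stop are placed there, including those that occur off drug.
- **Denominators.** The exposure-adjusted AE rate, which belongs to the primary safety analysis, and the two negative binomial models use time that includes the gap.

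The protocol describes restarting as a response to worsening after a stop for improvement. The misallocated time is therefore not a random sample of study time, although the documents give no effect size.

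**Working it through.** The plan gives no figure for overlap, gap length or number of restarters, so there is none to reproduce. The check applies the SAP's rules to assumed dates.

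**Inputs.** From SAP 6.2.4, Week 0 is day 1, Week 24 is day 169, Week 48 is day 337 and Week 96 is day 673. Assumed: first stop on day 169, restart on day 337, last stop on day 645 (Week 92: 92 × 7 + 1). The SAP's 28-day cover is credited after each stop.

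**Periods (SAP 6.2.2, stop date read as the last stop)**

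- Observation: day 1 to 645 + 28 = 673.
- Follow-up: day 169 + 29 = 198 to 673.
- Overlap: 673 − 198 + 1 = 476 days (68 weeks).
- Sum of the two periods: 673 + 476 = 1,149 days for a participant with 673 days in the study.

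**Off-drug time beyond the cover**

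- Days 198 to 336: 336 − 198 + 1 = 139 days (about 20 weeks).

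**Exposure (SAP 6.2.3)**

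- Formula: 645 − 1 + 29 = 673 days.
- Treated intervals: days 1–197 (197 days) plus days 337–673 (337 days) = 534 days.
- Ratio: 673 / 534 = 1.26, that is +26%.

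**Offset (SAP 4.3.1.2.3 and 4.3.1.2.4)**

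- (645 + 28 − 1) + 1 = 673 days, or 673 / 365.25 = 1.84 years, with the same 139-day gap inside it.

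**Other assumed patterns, last stop on day 645 throughout**

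| First stop | Restart | Overlap (days) | Gap (days) | Exposure ratio |
|---|---|---|---|---|
| 169 | 225 | 476 | 27 | 1.04 |
| 169 | 337 | 476 | 139 | 1.26 |
| 337 | 505 | 308 | 139 | 1.26 |
| 169 | 421 | 476 | 223 | 1.50 |
| 85 | 589 | 560 | 475 | 3.40 |

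**Cohort level.** Assume 120 participants with 673 exposure days each, and a 139-day gap for each of k restarters. The off-drug share of total exposure is k × 139 / (120 × 673): 0.17% for k = 1, 0.86% for k = 5, 1.72% for k = 10 and 3.44% for k = 20.

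**Stop date read as the first stop.** Observation is then days 1–197, follow-up is days 198–673, and the overlap is zero. SAP 6.2.3 still refers to the overall stop date, so exposure stays at 673 days. The observation-period AE rate would set events from 197 days against 673 days of exposure, a denominator 673 / 197 = 3.4 times too long for that participant.

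**The case against.** The best defence is that the overlap rests on a reading. The defining sentence does not say which stop date it means; last appears only in the missing-date rule, and overall only in SAP 6.2.3. Much else points to periods that were meant to abut: the +28 and +29 day offsets, the diagram in 6.2.2 that shows observation (D) followed by follow-up (E), the follow-up definition in 6.1.1, and the statement in SAP 1.2 that re-treated participants remain in follow-up. On that view the author meant the first stop, or wrote study withdrawal where treatment withdrawal was intended.

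This is good evidence of intent, and the point should not be put as a certain overlap. But the sentence uses first for one group and leaves it out for the other, and the next rule speaks of the last stop date. A programmer following the text would most naturally use the last stop. The exposure problem remains on either reading.

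A reader might also infer that AEs and hospitalizations are counted twice. The SAP does not support that. SAP 4.2.2 reports AEs by observation and total period, with no follow-up-only table, and nothing says the total is formed by adding the two periods. The hospitalization and visit rates are calculated for the observation and retrospective periods only. For these endpoints the fault is misplacement. Protocol 4.5 does ask for a follow-up AE summary; if it were produced under these definitions, AEs would appear in both tables.

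The last objection is materiality. The study is descriptive, it enrols patients whose physician has decided to continue Nucala, and restarting is described only after a stop for improvement. This limits the importance of the point but does not remove it.

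**Conclusion.** The point holds for participants who stop, stay in the study and restart, and only for them. On the natural reading of SAP 6.2.2 their periods overlap, contrary to Protocol 3.1, SAP 1.2 and the SAP's own diagram. On either reading of the stop date, the exposure formula counts the off-drug gap as treated time. The offsets subtract no gap either, and their missing-date rule likewise points to the last administration.

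In the assumed case, 476 days are in both periods and that participant's exposure is overstated by 26%. Comparing 96 with 72 weeks would suggest 33%, but that drops the 28-day cover which the SAP credits after a stop.

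It would be wrong to infer that the overall AE rate is seriously distorted. The documents do not say how many participants restart, and with up to 10 restarters and a 139-day gap the off-drug share is below 2% of cohort exposure. The point matters more for the follow-up and relapse summaries, to which probably few participants contribute, and because two programmers could derive different periods and denominators from the same text. It should be corrected, but it does not threaten the study's main conclusions.

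**What to change.** - **SAP 6.2.2:** end the observation period at the first treatment discontinuation date + 28 days for everyone who discontinues, whether or not they leave the study. Assign all later time and events, including re-treatment, to follow-up, as Protocol 3.1 and SAP 1.2 already say.
- **SAP 6.2.3:** compute exposure as the sum of treated intervals, each with its 28-day cover and without overlap, and split it by period. Observation-period AE rates then use only observation-period exposure, and total-period rates use all treated intervals. In the example these are 197 and 534 days. Summing intervals without the split would put re-treatment time in the observation denominator while its events are counted elsewhere.
- **SAP 4.3.1.2.3 and 4.3.1.2.4:** for participants who discontinue, end both the event count and the offset at the same first-discontinuation + 28 days. In the example the offset becomes 197 / 365.25 = 0.54 years.

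The cost is a wording change and a small change to the derivations. No new data item should be needed, because the schedule of activities in Protocol Appendix 1 already collects Nucala administration status in follow-up when re-treatment is given.

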6.2.3. Study Day and Nucala Stop Date

The study day will be calculated relative to visit date of Week 0 and as the number of days from Week 0:

- Ref Date = Missing then Study Day = Missing
- Ref Date < Week 0 then Study Day = Ref Date Week 0
- Ref Date \geq Week 0 then Study Day = Ref Date (Week 0) + 1

The duration of exposure to Nucala is calculated as (Nucala stop date – Nucala start date + 29). If overall Nucala stop date is missing, the last Nucala start date will be imputed.

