#### **Observation period**

During the observation period, which is scheduled for 96 weeks (approximately 2 years) at maximum, safety and effectiveness data are obtained at approximately 12-week intervals. The intervals may be shorter/longer or may be irregular depending on the usual pattern of healthcare visits.

Any data collected during the observation period are entered into eCRF. The assessments in the routine clinical practice during the observation period are shown in Section 9.1 (Appendix 1).

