# 6.2.1. Time Period and Frequency for Collecting AE and SAE Information

All AEs should be monitored throughout the study. All AEs and SAEs must be recorded in the eCRF.

All AEs and SAEs will be collected from the signing of the informed consent form until the final study visit.

All SAEs will be recorded and reported to the sponsor or designee within 24 hours of recognition, as indicated in Section 9.3 (Appendix 3). The investigator will submit any updated SAE data to the sponsor within 24 hours of it being available. AEs related to Nucala will be recorded and reported to the sponsor or designee within 5 work days of recognition.

Investigators are not obligated to actively seek AE/SAEs after the conclusion of the study participation. However, if the investigator learns of any SAE, including a death, at any time after a participant has been discharged from the study, and they consider the event to be reasonably related to Nucala, the investigator must promptly notify the sponsor. As for death information, investigators are asked to report it to the sponsor throughout the study period regardless of whether the death is related to Nucala or not.

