The summary be provided for AESI. The percentage will be calculated in two ways; one with number of participants with event as the denominator and the other with total number of participants as the denominator. The worst-case approach will be applied at participant level for the maximum intensity (i.e. a participant will only be counted once as the worst case from all the events experienced by the participant). For action taken to an event, a participant will be counted once under each action (e.g. if a participant has an event leading to both study discontinuation and dose reduction, the participants will be counted once under once under both actions).

Listings of all AEs and of subject numbers for individual AEs will be displayed. Reasons for considering as a SAE, AEs leading to withdrawal from study and AESIs will also be listed. In addition, patient profiles will be provided of patients with deaths.

Exposure-adjusted AE rate (the number of events per 1000 participant-years of exposure) for the AEs will also be summarized. This summary table will be produced by the

observation period and the total period (the observation period and the follow-up period), respectively.

The number of events per 1000 participant-years of exposure will be calculated as:

 $(1000 \times \text{number of AEs during the period}) / (total duration of exposure in days / 365.25)$

The derivation of the total duration of exposure in days is defined in 6.2.3.

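### The uncapped 28-day exposure tail puts time without routine AE collection into the observation-period AE rate (0% to 4.0% too low for a completer), and the total-period rate needs its own denominator

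*SAP*

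**What the plan says.** SAP 4.2.2 plans an AE rate per 1000 participant-years, for the observation period and for the total period (observation plus follow-up). It divides the AE count by "total duration of exposure in days / 365.25" and points elsewhere for the denominator: "The derivation of the total duration of exposure in days is defined in 6.2.3".

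SAP 6.2.3 then says: "The duration of exposure to Nucala is calculated as (Nucala stop date – Nucala start date + 29". The 29 is the usual inclusive day plus 28 days. For a missing date: "If overall Nucala stop date is missing, the last Nucala start date will be imputed". This suggests that the stop date is the date of the last injection, but the section does not say so. Nor does it say what the stop date is for someone who completes the study and carries on with marketed Nucala.

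SAP 6.2.2 ends the observation period 28 days after the stop date for participants who do not withdraw, and otherwise at "the first treatment discontinuation date +28 days for the participants who withdraw from study".

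Protocol 6.2.1 sets the collection window: "All AEs and SAEs will be collected from the signing of the informed consent form until the final study visit". It adds: "Investigators are not obligated to actively seek AE/SAEs after the conclusion of the study participation". Protocol 3.3.3 asks that participants who stop Nucala be followed to planned Week 96 where possible.

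The event-rate models in SAP 4.3.1.2.3 and 4.3.1.2.4 use another rule. Treatment time is end minus start plus 1 for participants who complete the study, and 28 days are added only for those who enter follow-up.

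**The concern.** Person-time belongs in a rate's denominator only if an event in it would have been picked up. The 28-day tail meets that test while the participant is still under observation. SAP 6.2.2 and 6.2.3 do not ask whether that is so: they stop neither at last contact nor at death.

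Two groups can fall outside. The first is completers with a recent dose. The label interval is 4 weeks (Protocol 3.1) and 672 / 28 = 24 exactly, so a participant on schedule from Week 0 is due a dose at Week 96, a visit at which administration status is recorded (Protocol 9.1). If that dose is the recorded stop date, the whole tail lies after the final visit. The second is participants who leave the study or die within 28 days of a dose.

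Long-term safety is the primary objective, this rate is one of its planned summaries, and SAP 4.2.3 has no sensitivity analysis. In the observation-period table the tail can only lower the rate or leave it unchanged.

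**Working it through.** The documents state no person-time or AE rate, so there is no plan figure to reproduce for this point. The plan's sample size does reproduce: ln(0.20)/ln(0.985) = 106.5, so 107; 107/0.90 = 118.9, so 119, or about 120. It does not depend on exposure.

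**Inputs.** Tail of 28 days (SAP 6.2.3); Week 96 = Day 673 (SAP 6.2.4); dosing interval of 28 days (Protocol 3.1); about 120 participants with 10% dropout (SAP 5). Assumptions: the start date is the Week 0 dose (Day 1), the stop date is the last recorded dose, and the AE rate is constant over time.

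**Completer, final visit on Day 673.** SAP exposure = stop − 1 + 29. Observed time = 673 days. Understatement = 1 − 673 / SAP exposure.

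| Last dose before final visit | SAP exposure (days) | Rate too low by |
|---|---|---|
| 0 days (Week 96) | 701 | 28/701 = 4.0% |
| 7 days | 694 | 21/694 = 3.0% |
| 14 days | 687 | 14/687 = 2.0% |
| 21 days | 680 | 7/680 = 1.0% |
| 28 days (Week 92) | 673 | 0% |

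Upper end, 120 completers all dosed on Day 673: 120 × 701 / 365.25 = 230.3 participant-years against 120 × 673 / 365.25 = 221.1. A true rate of 1000 per 1000 participant-years would print as 1000 × 673/701 = 960.

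**Participant who leaves the study on a dosing day.** Day 85: 28/113 = 24.8%. Day 169: 28/197 = 14.2%. Day 337: 28/365 = 7.7%. Each figure is for that participant alone. In a pooled denominator of about 77,000 days, one such person adds 28 days, or 0.04%.

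**Participant who stops Nucala and is followed for at least 28 more days.** The tail is observed, so 0%.

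**Cohort example.** Assume that 12 of 120 stop Nucala on Day 337, are not re-treated and are followed to Week 96, and that the other 108 have a last dose on Day 673.

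- SAP denominator: 108 × 701 + 12 × 365 = 80,088 days.
- Observed observation-period time: 108 × 673 + 12 × 365 = 77,064 days. Rate factor 77,064 / 80,088 = 0.962, so 3.8% too low.
- Observed total-period time: 120 × 673 = 80,760 days. The SAP divides all these AEs by the same 80,088 days: 80,760 / 80,088 = 1.008, so 0.8% too high.
- If the completers' last dose is at Week 92, or if the tail is capped and nothing else changes, the denominator is 77,064: 80,760 / 77,064 = 1.048, so the total-period rate is 4.8% too high.

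If the 12 instead leave the study on Day 337, a dosing day, observed time is 108 × 673 + 12 × 337 = 76,728 days. Then 76,728 / 80,088 = 0.958, so the rate is 4.2% too low. This is a worst case: it needs every completer dosed on the final visit and every dropout leaving on a dosing day, although Protocol 3.3.3 asks for continued follow-up.

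**The case against.** The strongest defence is that the tail is deliberate and matched. It equals one dosing interval, the SAP's revision table says that version 5.0 aligned the period definition with a standard exposure definition, and 6.2.2 extends the AE counting window by the same 28 days. That disposes of any claim that the two windows are defined differently. It does not supply ascertainment: a counting window that outlasts routine collection still adds days without adding events.

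It is also fair that the primary endpoints are frequencies, so counts and percentages are untouched, and that the study is descriptive. With, say, 100 events the 95% interval is about ±1.96/√100 = ±20%, far wider than 4%. This limits the importance of the point but does not remove a systematic error.

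Three stronger readings are tempting and not supported.

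- A reader might infer that every exposure-adjusted rate is understated. The total-period rate also counts follow-up AEs over Nucala exposure alone, which pushes it upward and can outweigh the tail.
- A reader might infer that no AE can be recorded in the tail. Protocol 6.2.1 requires notice of related serious AEs learned of after discharge, and Protocol 9.3.4 allows late reports on paper. Only routine collection stops.
- A reader might treat running past Week 96 as an error in itself, because the observation period is one "which is scheduled for 96 weeks (approximately 2 years) at maximum". But the schedule allows ±4 weeks and SAP 6.2.4 accepts a Week 96 visit up to Day 701. What matters is the gap between last recorded dose and last contact.

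**Conclusion.** The point holds for the observation-period rate, in limited form. Completers last dosed less than 28 days before the final visit, and participants who leave or die within 28 days of a dose, bring in person-time without routine AE ascertainment. The understatement is 0% to 4.0% for a Week 96 completer. It is larger for an individual early leaver, with little effect on the pooled rate. It is nil for participants who stop Nucala and stay in follow-up.

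Where in that range the study falls cannot be fixed from the documents, because the stop date of a continuing completer is undefined. The figures assume the Week 0 dose as start and a final visit on Day 673.

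For the total-period rate no single direction can be stated: +0.8% or +4.8% in the examples above, and −4.0% if nobody stops Nucala and all are dosed at Week 96. Its denominator is unsuitable for a separate reason.

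The SAP also contradicts itself: its event-rate offsets give completers no tail, while 6.2.2 and 6.2.3 give one to everyone. The contrast holds only for recorded end dates, since 4.3.1.2.3 and 4.3.1.2.4 impute last administration plus 28 days when the end date is missing.

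**What to change.** 1. In SAP 6.2.3, define the Nucala start and stop dates, including the stop date for a completer who continues marketed Nucala and whether a dose at the Week 96 visit counts.
2. In 6.2.2 and 6.2.3, end the observation period and exposure at the earlier of stop date + 28 days and the date of last study contact (final visit, withdrawal visit or death). Use an actual recorded date, not the Week 96 date that 6.2.4 imputes for early withdrawals. Use the result for the observation-period rate in 4.2.2.
3. For the total-period rate, use observed person-time from the Week 0 dose to last study contact, follow-up included. Step 2 must not be applied to this table alone, because the cap without this change raises the overstatement (from 0.8% to 4.8% in the example).
4. Reconcile the treatment-time offsets in 4.3.1.2.3 and 4.3.1.2.4, and their missing-date rule, with 6.2.2 and 6.2.3.

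The cost is a few lines of SAP text and derivation code, with no new data. Observation-period rates may become up to about 4% less favourable. Counts, percentages and the sample size do not depend on the denominator.
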